9.7.2.2. Descriptive analyses

For the descriptive analyses, the number of observations, mean, standard deviation, median, interquartile range, and range will be presented for continuous variables, and the number and percentage of patients in each category will be presented for categorical variables. In addition to all characteristics reported in the interim reports, the study cohorts will be described according to the covariates listed in Section 9.3.3. Characteristics will be reported separately

for those with and without COVID-19 diagnoses prior to cohort medication exposure, as well as by hospitalization status at the time of the start of the COVID-19 episode associated with treatment (if applicable).

Crude prevalence estimates and corresponding 95% CIs for pregnancy outcomes, and separately for infant outcomes, will be calculated using robust Poisson regression models, with the denominator for the pregnancy outcomes being the number of pregnancies from which the cases arose, the denominator for the infant outcomes being the number of linked livebirths, and the numerator being the number of cases, as described in Table 4. Logbinomial regression models will be included as sensitivity analyses.

Table 4. Statistical Analyses of Study Outcomes

Outcome	Measure of Frequency	Measure of Association (Regression Model)	Timing of Outcome Ascertainment	Unit of Analysis
SA	Prevalence	Prevalence ratio (Poisson)	Before Week 20 of pregnancy	Pregnancy
Induced termination	Prevalence	Prevalence ratio (Poisson)	Before Week 20 of pregnancy	Pregnancy
Stillbirth	Prevalence	Prevalence ratio (Poisson)	At or after Week 20 of pregnancy	Pregnancy
Livebirth	Prevalence	Prevalence ratio (Poisson)	At end of pregnancy	Pregnancy
MCM	Prevalence	Prevalence ratio (Poisson)	At birth or during infant follow-up	Linked livebirths
SGA	Prevalence	Prevalence ratio (Poisson)	At birth or during infant follow-up	Linked livebirths
Preterm birth	Prevalence	Prevalence ratio (Poisson)	At birth or during infant follow-up	Linked livebirths
Postnatal growth deficiency	Prevalence	Prevalence ratio (Poisson)	At birth or during infant follow-up	Linked livebirths
Infant developmental delay	Prevalence	Prevalence ratio (Poisson)	At birth or during infant follow-up	Linked livebirths

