9.5. Study size

The planned sample size incorporates several assumptions derived from published literature, including the following approximate prevalence of pregnancy outcomes:

- Under 1% of pregnancies result in stillbirth (FDA 2002)
- 14% of pregnancies result in SA or miscarriage (FDA 2002)
- 18% of pregnancies have historically been expected to end in induced termination (Jones et al. 2017)
- 3% of live born infants have a major birth defect in the US each year (March of Dimes 2015)
- 10% of live born infants are born preterm or SGA (CDC 2008, Ferré et al. 2016)

Based on these reference percentages, the following assumptions were made for sample size calculation:

- $\alpha = 0.05$
- Power=0.8
- 1:2 matching
- Outcome prevalence as cited above

Table 1 and Table 2 show the minimum required number of PAXLOVID-exposed pregnancies required to proceed to the secondary objective of comparative analyses. Comparative analyses will be conducted if the sample size to detect a RR > 2.0 is achieved for each outcome; target sample size may be achieved for some outcomes but not others.

To detect a RR > 2.0 at 80% power a minimum of 127 PAXLOVID-exposed pregnancies are required for SA, 251 for SGA and preterm birth, and 2,212 for stillbirth, the rarest of the outcomes (Table 1). A minimum of 938 PAXLOVID-exposed pregnancies during the first trimester are required for the primary outcome of MCM (Table 2).

Fewer PAXLOVID-exposed pregnancies are required to detect an RR of > 2.5 at 80% power: 63 for SA, 127 for SGA and preterm birth, and 1,142 for stillbirth. For MCM, the minimum number of pregnancies with PAXLOVID exposure during the first trimester is 482. These estimates are based on 1:2 matching; however, the analyses for this study will utilize IPTW for confounding adjustment. Sample size calculations are based on 1:2 matching as a conservative estimate due to the retention of all eligible pregnancies in IPTW. Power for the analysis of induced termination will be similar to that for SA. The majority of pregnancies end in livebirth; therefore, power is expected to be adequate for this outcome.

Table 1. Sample Size Required for 80% Power to Detect Relative Risks (As or More Extreme) for Pregnancy Outcomes, with 1:2 Matching

Outcome	Prevalence of Outcome	RR	PAXLOVID-Exposed Pregnancies with Observed Outcomes Needed*	PAXLOVID-Exposed Pregnancies Needed**
SA	14%	2	101	127
		2.5	50	63
Stillbirth	1%	2	1,769	2,212
		2.5	913	1,142

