^{*} Sample size calculated using PROC POWER function in SAS with a two-sided likelihood ratio chi-square test, and the specified relative risk and prevalence in the unexposed (SAS EG V8.2, SAS Institute Inc., Cary, NC).

Table 2. Sample Size Required for 80% Power to Detect Relative Risks (As or More Extreme) for Infant Outcomes, with 1:2 Matching

Outcome	Prevalence of Outcome	RR	PAXLOVID- Exposed Livebirths Needed*	PAXLOVID- Exposed Pregnancies Needed**
MCM	3%	2	572	938
		2.5	294	482
Preterm birth	10%	2	153	251
		2.5	77	127
SGA	10%	2	153	251
		2.5	77	127

^{**} A divisor of 0.80, which is the proportion of ongoing pregnancies for which an outcome is eventually observed in DAPI, was used to calculate the number of exposed pregnancies needed.

Table 2. Sample Size Required for 80% Power to Detect Relative Risks (As or More Extreme) for Infant Outcomes, with 1:2 Matching

Outcome	Prevalence of	RR	PAXLOVID-	PAXLOVID-
	Outcome		Exposed	Exposed
			Livebirths	Pregnancies
			Needed*	Needed**

^{*} Sample size calculated using PROC POWER function in SAS with a two-sided likelihood ratio chi-square test and the specified relative risk and prevalence in the unexposed (SAS EG V8.2, SAS Institute Inc., Cary, NC).

Following initial accrual results from the first interim report, it was observed that fewer Cohort 2 pregnancies were accrued than PAXLOVID-exposed pregnancies, at a ratio of approximately 5:1, suggesting that matching of 2 comparators to each PAXLOVID pregnancy is unlikely to be feasible. Assuming a final ratio of 5 PAXLOVID-exposed pregnancies to each Cohort 2 pregnancy, a minimum sample size of 3,352 PAXLOVID-exposed pregnancies (and 670 Cohort 2 pregnancies) will be required to be accrued during the first trimester exposure window to detect a RR \geq 2.0 at 80% power for MCM. To detect a RR \geq 2.5, 1,664 PAXLOVID-exposed pregnancies (and 333 Cohort 2 pregnancies) will be required.

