Table 3 provides counts of total pregnancies, COVID-19 positive pregnancies, and pregnancies exposed to COVID-19 treatments within the ORD in 2020-2022. While 200,000 pregnancies are typically identified in any given calendar year within the ORD, this number has dropped slightly during the COVID-19 pandemic, as seen in Table 3 with roughly 180,000 pregnancies identified in 2020 and 2021. The counts include complete data through mid-2022; thus, some pregnancies in the latter half of 2022 may not be captured. Between 2020 and mid-2022, 35,303 of 460,062 pregnancies (7.7%) had a COVID-19 diagnosis code. Of the 35,303 COVID-19 positive pregnancies, 409 (1.2%) of pregnancies were exposed to bebtelovimab, while 382 (1.1%) were exposed to remdesivir. A total of 1,021 pregnancies were exposed to PAXLOVID, with roughly half of these also being diagnosed with COVID-19.

Annual interim reports will provide information on the uptake of PAXLOVID and the ability to reach adequate sample size for the study outcomes. If needed, a data partner may be added to increase statistical power (Section 9.4.4) to conduct the comparative analysis of MCM, per the secondary study objective. Even with multiple data partners, power may not be adequate for the assessment of stillbirth due to its rarity.

Table 3. Counts of Total and COVID-19 Positive Pregnancies in the Optum Research Database, 2020-2022

	2020	2021	2022	Total
			(partial) ^a	
All pregnancies	182,835	179,058	98,169	460,062

^{**} A divisor of 0.61, which is the proportion of ongoing pregnancies for which an outcome is eventually observed and the outcome is a livebirth in DAPI, was used to calculate the number of total exposed pregnancies needed.

^{***}Minimum sample size refers to the pregnancies with first trimester exposure

Table 3. Counts of Total and COVID-19 Positive Pregnancies in the Optum Research Database, 2020-2022

	2020	2021	2022	Total
			(partial) ^a	
Pregnancies with ≥1 PAXLOVID		295	726	1,021
dispensing				
Pregnancies with ≥1 COVID-19	10,337	19,581	5,385	35,303
diagnosis code				
Subset of pregnancies with ≥1		185	379	564
COVID-19 diagnosis code and ≥1				
PAXLOVID dispensing				
Subset of pregnancies with ≥1		184	225	409
COVID-19 diagnosis code and ≥1				
bebtelovimab administration				
Subset of pregnancies with ≥1	165	206	11	382
COVID-19 diagnosis code and ≥1				
remdesivir administration				

a Data for 2022 is approximately complete through June 2022.

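### The models that Section 9.7.2.2 names for crude cohort prevalence give no 95% CI at zero events; this matters only in sparse cells and needs a one-sentence fallback (minor)

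*Protocol*

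**What the plan says.** Protocol Section 9.7.2.2 fixes one method for every cohort-level risk: "Crude prevalence estimates and corresponding 95% CIs for pregnancy outcomes, and separately for infant outcomes, will be calculated using robust Poisson regression models". For MCM and the other infant outcomes it specifies "the denominator for the infant outcomes being the number of linked livebirths". The only alternative it names is this: "Logbinomial regression models will be included as sensitivity analyses". The protocol gives no exact or score interval and no rule for a cell with zero events.

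The primary objective (Section 8) is to estimate the MCM risk in each of the three cohorts. Section 9.5 makes only the comparative analyses depend on reaching a target size. Section 9.7.2 has the prevalence in each cohort described without that condition.

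On rarity, Section 9.5 states "Under 1% of pregnancies result in stillbirth" and "3% of live born infants have a major birth defect in the US each year". It also accepts that "power may not be adequate for the assessment of stillbirth due to its rarity". On Cohort 2, it reports that "fewer Cohort 2 pregnancies were accrued than PAXLOVID-exposed pregnancies, at a ratio of approximately 5:1".

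**The concern.** A robust Poisson model for a single proportion gives a Wald interval on the log scale. With zero events the estimate is log(0), which has no finite value and no usable standard error, so there is no upper limit. The log-binomial model has the same link and fails in the same way, so the sensitivity analysis does not fill the gap.

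In a safety study, the upper limit is the informative result when no events are seen. The smallest cohort is Cohort 2 in the first-trimester window, and its risks will be tabulated however few pregnancies accrue. If a cell there has no events, the method as written leaves it without the 95% CI that the section promises.

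**Working it through.** **Plan's own figures.** The protocol states no interval coverage and no expected event count for Cohort 2, so there is no such figure to reproduce. It does give required first-trimester Cohort 2 sizes for MCM of 670 (RR 2.0) and 333 (RR 2.5). I take these as stated. With five exposed per comparator, a likelihood-ratio calculation gives about 774 and 400 instead. That is a separate matter, and larger cohorts would only weaken the present point.

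**Inputs.**
- MCM 3% and stillbirth 1% (Section 9.5, Tables 1 and 2).
- Pregnancies with an observed outcome 0.80; pregnancies ending in an observed livebirth 0.61 (Section 9.5, table footnotes).
- Infant linkage 85% (Section 9.4.2).
- Share available for record validation 35% to 42.5% (Section 9.3.1.3). I use 40%, which is an assumption within that range.
- Cohort 2, first trimester, upper value: 333 pregnancies.
- Cohort 2, first trimester, lower value: about 200 pregnancies, an assumption. Table 3 shows 409 bebtelovimab pregnancies and 206 + 11 = 217 remdesivir pregnancies in 2021-2022. The sum is 626, and an assumed one-third first-trimester share gives 209, rounded to 200.

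**Denominators.**
- Stillbirth: 200 x 0.80 = 160; 333 x 0.80 = 266.
- Linked livebirths: 200 x 0.61 x 0.85 = 104; 333 x 0.61 x 0.85 = 173; 670 x 0.61 x 0.85 = 347.

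**Formulas.** For x events in n, with p̂ = x/n, the planned interval is p̂ x exp(±1.96 x sqrt((1 − p̂)/x)). At 10/347 this is 1.6% to 5.3%, which agrees with a fitted robust Poisson model. At 0/347 the fit stopped with an error. The chance of having no interval is (1 − p)^n. Coverage is the exact binomial sum over x, with x = 0 counted as not covering.

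| Cell | n | Expected events | P(no interval) | Coverage | Coverage given at least 1 event |
|---|---|---|---|---|---|
| Stillbirth 1% | 160 | 1.6 | 0.99^160 = 20% | 77.7% | 97.1% |
| Stillbirth 1% | 266 | 2.7 | 0.99^266 = 7% | 87.8% | 94.3% |
| Confirmed MCM 1.2% | 104 | 1.2 | 0.988^104 = 28.5% | 67.8% | 94.8% |
| Confirmed MCM 1.2% | 173 | 2.1 | 0.988^173 = 12.4% | 81.7% | 93.3% |
| Overall MCM 3% | 104 | 3.1 | 0.97^104 = 4.2% | 92.0% | 96.1% |
| Overall MCM 3% | 173 | 5.2 | 0.97^173 = 0.5% | 95.8% | 96.3% |
| Overall MCM 3% | 347 | 10.4 | below 0.1% | 95.8% | 95.8% |

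The last column shows that the shortfall is almost wholly the missing interval at zero. Averaged by expected events, coverage is 83% at two, 91% at three, 95% at four and about 96% at five.

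**Effect of the fix.** Clopper-Pearson at 0/160 has upper limit 1 − 0.025^(1/160) = 2.3%. If it is used for five or fewer events and the planned interval otherwise, exact enumeration gives coverage between 94.4% and 99.1% in all seven rows.

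**The case against.** The strongest reply is that an empty cell misleads nobody. The count and denominator remain visible, and Section 9.7 leaves detailed methods to an SAP that may modify the plan, so a zero-cell rule could well appear there. That stands, and it is why the point is minor. The protocol nevertheless names the method for these intervals, and both models it names fail at zero.

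A reader might infer more than the document supports:

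- **That robust Poisson intervals generally under-cover at low counts.** Given at least one event, they cover about 93-97%. Low overall coverage is the zero-event fault counted a second time.
- **That the primary MCM interval is unreliable in Cohort 2.** At 3% and the protocol's own sizes it is nominal. The worse MCM figures need a confirmed-cases-only rule, which Section 9.7.2.3 states for the primary comparative analyses. Section 9.7.2.2 does not state it for descriptive risks.
- **That MCM by body system will fail.** An assumed 0.3% defect in 347 infants would have no interval in 0.997^347 = 35% of samples. But Section 9.3.1.2 promises counts and classification by body system, Section 9.7.2.3 makes subtype analyses depend on numbers, and Table 4 lists MCM only as a whole.
- **That few Cohort 2 events are expected.** The protocol does not say so. Table 3 is complete only to about June 2022, while accrual runs to December 2025. Against that, bebtelovimab use ended in November 2022 and Cohort 2 requires outpatient administration, so the final size is uncertain in both directions.

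Section 9.1 also suggests the full pregnancy window for pregnancy outcomes. There, 626 x 0.80 = 501 pregnancies give 5.0 expected stillbirths, a 0.7% chance of no interval and 96.2% coverage.

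**Conclusion.** The point holds in narrow form and is minor. It is certain that the named main and sensitivity models give no interval at zero events, and that the descriptive risks they serve carry no sample-size condition. How often this would bite depends on assumptions: 200 to 333 first-trimester Cohort 2 pregnancies, independent pregnancies and, for the MCM range of 12% to 29%, confirmed cases only at 40% of 3%. With those assumptions the problem is confined to cells expecting about three or fewer events. The document does not support replacing robust Poisson throughout, because the method performs well elsewhere and Section 9.7.2.3 relies on robust standard errors for repeat pregnancies.

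**What to change.** Add one sentence to Section 9.7.2.2, and mirror it in the SAP: where a cohort has zero or few events for an outcome (for example five or fewer), the crude prevalence 95% CI is a Clopper-Pearson or Wilson interval. Choose one of the two and fix the threshold in advance. Keep robust Poisson with clustered standard errors for all other cells and for the prevalence ratios.

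The cost is small. Clopper-Pearson intervals are slightly wide, and both replacements ignore the modest clustering from repeat pregnancies in the same woman, which should have little effect in cells with so few events.

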9.3.1.1. Pregnancy outcomes

The pregnancy outcomes to be assessed are:

- SA defined as the loss of pregnancy before the 20th week of gestation
- Induced termination defined as an intervention to end a pregnancy so that it does not result in a livebirth
- Stillbirth defined as the loss of pregnancy at or after the 20th week of gestation
- Livebirth a delivered fetus with any sign of life (eg, voluntary movement, heartbeat) regardless of gestational weeks

Lists of ICD-10 diagnostic codes are provided in ANNEX 2. ADDITIONAL INFORMATION.

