9.7.2.3. Comparative safety analyses

The comparative analysis will estimate prevalence ratios and corresponding 95% CIs for each of the pregnancy or infant events comparing the PAXLOVID exposed pregnancy cohorts to the comparator pregnancy cohorts in the same exposure window (eg, Cohort 1 first trimester cohort versus Cohort 2 first trimester cohort; Cohort 1 first trimester cohort versus Cohort 3 first trimester cohort). Prevalence will be estimated for these outcomes because they develop during gestation but are only observable at birth; thus, only the prevalence at birth

can be calculated. Crude (unadjusted) and IPTW-adjusted prevalence ratios will be reported along with corresponding 95% CIs. The prevalence ratios will be estimated using robust Poisson regression models (Chen et al. 2018), with analysis of log-binomial models as sensitivity analysis.

Analyses based on claims-identified cases will be presented. However, the primary comparative analyses in the final report will only include outcomes that have been confirmed via medical record review or identified via published validated algorithms.

Planned analyses for each outcome are described in Table 4.

Comparative analyses will be performed overall and among subgroups according to presence of COVID-19 diagnoses occurring prior to exposure to cohort medications, as well as by hospitalization status at the time of COVID-19 diagnosis, sample size permitting.

Analyses will be conducted on MCMs collectively as a whole, with subgroup analyses by MCM subtype (for example, organ system affected) performed as sample size allows. The number of pregnancies with each outcome will serve to guide the analyses that are feasible.

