- HCPCS S0190 Mifepristone ORAL 200 mg
- HCPCS S0191 Misoprostal oral 200 mcg
- HCPCS S0199 Medically induced abortion by oral ingestion of medication including all associated services and supplies
- HCPCS S2260 Induced abortion, 17-24 weeks
- HCPCS S2262 Abortion for maternal indication, 25 weeks or greater
- HCPCS S2265 Induced abortion, 25-28 weeks
- HCPCS S2266 Induced abortion, 29-31 weeks
- HCPCS S2267 Induced abortion, 32 weeks/greater
- CPT 01964⁵ Anesthesia for abortion procedures
- CPT 01965 Anesthesia for incomplete or missed abortion procedures
- CPT 01966 Anesthesia for induced abortion procedures
- CPT 59840 Induced abortion, by dilation and curettage
- CPT 59841 Induced abortion, by dilation and evacuation
- CPT 59850 Induced abortion, by 1 or more intra-amniotic injections (amniocentesis-injections), including hospital admission and visits, delivery of fetus and secundines;
- CPT 59851 Induced abortion, by 1 or more intra-amniotic injections (amniocentesis-injections), including hospital admission and visits, delivery of fetus and secundines; with dilation and curettage and/or evacuation
- CPT 59852 Induced abortion, by 1 or more intra-amniotic injections (amniocentesis-injections), including hospital admission and visits, delivery of fetus and secundines; with hysterotomy (failed intra-amniotic injection)
- CPT 59855 Induced abortion, by 1 or more vaginal suppositories (eg, prostaglandin) with or without cervical dilation (eg, laminaria), including hospital admission and visits, delivery of fetus and secundines;
- CPT 59856⁶ Induced abortion, by 1 or more vaginal suppositories (eg, prostaglandin) with or without cervical dilation (eg, laminaria), including

⁵ CPT copyright 2022 American Medical Association. All rights reserved.

⁶ CPT copyright 2022 American Medical Association (AMA). All rights reserved.

hospital admission and visits, delivery of fetus and secundines; with dilation and curettage and/or evacuation

CPT 59857 Induced abortion, by 1 or more vaginal suppositories (eg, prostaglandin) with or without cervical dilation (eg, laminaria), including hospital admission and visits, delivery of fetus and secundines; with hysterotomy (failed medical evacuation)

Stillbirth

- O31.2--- Continuing pregnancy after intrauterine death of 1 fetus or more
- O36.4--- Maternal care for intrauterine death
- P95 Stillbirth
- Z37.1 Single stillbirth
- Z37.3 Twins, 1 liveborn and 1 stillborn
- Z37.4 Twins, both stillborn

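### Table 4 limits induced termination to before week 20, contradicting the unlimited definition in Section 9.3.1.1 and the late-gestation codes in Annex 2

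*Protocol*

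**What the plan says.** Three places in the Protocol fix what counts as an induced termination.

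- **Section 9.3.1.1** defines it as "an intervention to end a pregnancy so that it does not result in a livebirth". No week is named. In the same list, spontaneous abortion is capped at week 20, and stillbirth is "defined as the loss of pregnancy at or after the 20th week of gestation".
- **Annex 2** lists the codes that identify it. They include "HCPCS S2265 Induced abortion, 25-28 weeks" and "HCPCS S2267 Induced abortion, 32 weeks/greater", as well as S2266 (29-31 weeks), S2262 (25 weeks or more, maternal indication) and S2260 (17-24 weeks).
- **Table 4 in Section 9.7.2.2** gives its timing of ascertainment as "Before Week 20 of pregnancy", the same entry as for spontaneous abortion.

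Table 4 is tied to the analysis twice. Section 9.7.2.2 describes the prevalence calculation with "the numerator being the number of cases, as described in Table 4", and Section 9.7.2.3 adds: "Planned analyses for each outcome are described in Table 4".

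**The concern.** A programmer who follows Table 4 will discard a termination at 26 weeks. One who follows Section 9.3.1.1 and Annex 2 will count it. Both would be following the Protocol. This is current text, not a leftover in the amendment log. Nor is it detail that a protocol leaves to the analysis plan, because the Protocol fixes the timing itself, against its own definition.

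Three things are at stake: the completeness of a secondary outcome, the category given to pregnancies terminated at or after week 20, and possibly the content of stillbirth. Stillbirth is the rarest outcome in the sample size section, and Section 9.5 already warns that power for it may be inadequate. Late terminations are also plausibly the ones that follow a detected anomaly, so in a malformation safety study their handling should not be left to chance.

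**Working it through.** The Protocol states no figure for late terminations, so there is none to reproduce. The check is a comparison of texts, followed by an illustration of size.

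**1. Definition and codes against Table 4.** Four of the listed codes lie wholly after week 20 and a fifth straddles it.

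| Code | Weeks covered | Can it yield a case under Table 4? |
|---|---|---|
| S2260 | 17-24 | Only in part |
| S2262 | 25 or more | Never |
| S2265 | 25-28 | Never |
| S2266 | 29-31 | Never |
| S2267 | 32 or more | Never |

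Listing codes that can never produce a case makes sense only if late terminations were meant to count.

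**2. Where a late termination would go.** Under Table 4 it is not an induced termination. It is not a spontaneous abortion, which ends at week 20, and it is not a livebirth. The wording of the stillbirth definition does not exclude an induced loss. However, the stillbirth code list in Annex 2 contains no termination codes, and Section 9.3.1.3 identifies stillbirth with a published algorithm. The pregnancy would therefore enter stillbirth only if it also carried a code such as O36.4 or Z37.1. Otherwise it has no outcome category.

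**3. Size.** Inputs from Section 9.5: 18% of pregnancies end in induced termination, and stillbirth is 1% (the Table 1 value). The share *s* of terminations at or after week 20 is not in the document. I assume 0.5% to 5%.

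- Late terminations as a share of pregnancies = 0.18 × *s*.
- Stillbirth rate if all are reclassified = 0.01 + 0.18 × *s*.
- Apparent stillbirth RR if the true RR is 2.0 and late terminations are equally frequent in both cohorts = (0.02 + 0.18 × *s*) / (0.01 + 0.18 × *s*).

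| *s* | Late terminations, % of pregnancies | Stillbirth rate, upper bound | Apparent stillbirth RR, all reclassified |
|---|---|---|---|
| 0.5% | 0.09% | 1.09% | 1.92 |
| 1% | 0.18% | 1.18% | 1.85 |
| 2% | 0.36% | 1.36% | 1.74 |
| 5% | 0.90% | 1.90% | 1.53 |

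The induced termination count falls by *s* itself, so a prevalence of 18% becomes 17.91% (18 − 0.09) to 17.10% (18 − 0.90). If *s* is equal in the two cohorts, the termination prevalence ratio does not change. If *s* sits at opposite ends of the range, the ratio is multiplied by 0.95/0.995 = 0.955 or by 0.995/0.95 = 1.047.

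**4. Malformations.** The main analysis uses linked livebirths (Table 4; Section 9.9), so terminations do not enter it. The sensitivity analysis promised in Section 9.9 covers malformations in spontaneous abortions, induced terminations and stillbirths alike. A case moved from termination to stillbirth stays within it. Only a case with no category at all falls out.

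**The case against.** The strongest defence is that the definition and the code list are the operative texts and that the Table 4 cell is only loosely descriptive. The same column places preterm birth and SGA at birth or during infant follow-up, although both are settled at birth. Section 9.3.1 also sends potential induced terminations to medical record adjudication, so a pregnancy billed with S2265 would be found and, where records can be obtained, adjudicated as a termination. On that reading nothing is lost.

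Part of this stands: loss is the result of applying Table 4 literally, not a certainty. But Sections 9.7.2.2 and 9.7.2.3 both point to Table 4 for the count and the analysis, so the literal reading has textual support and the contradiction remains.

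Two stronger readings are tempting and are not supported. A reader might infer that late terminations will be counted as stillbirths. The code list and the use of a published algorithm make that conditional on a co-recorded stillbirth code. A reader might also infer that the study loses its malformation signal. The main analysis never included these pregnancies, and the sensitivity analysis loses only those left without any category.

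A fair caution applies to the remedy. Excluding terminations from stillbirth could depart from the algorithm whose 83% PPV Section 9.3.1.3 relies on, and its rules are not visible in the Protocol.

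**Conclusion.** The contradiction is certain: Table 4 conflicts with Section 9.3.1.1 and with Annex 2. Applied as written, it drops terminations at or after week 20 from a secondary outcome and gives them no category.

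The numerical consequence rests on an assumed share of late terminations. Across 0.5-5%, the termination count changes little. The stillbirth rates of 1.09-1.90% and the attenuated RRs are ceilings that require every late termination to be reclassified, which the documents do not say will happen. The upper end also needs the 5% share.

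Only secondary outcomes are touched, so the severity is minor to moderate.

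**What to change.** In Table 4, change the timing for induced termination to any time during pregnancy, so that it matches Section 9.3.1.1 and the Annex 2 codes. Add a sentence to Section 9.3.1.1 that a pregnancy classified as an induced termination is not also counted as a stillbirth, once this has been checked against the published stillbirth algorithm cited in Section 9.3.1.3.

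If a week-20 limit is really intended, the definition and the code list must change instead, and late terminations need a named category.

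The cost is one table cell, one sentence and the check of the algorithm. No new data are needed.
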